## MEDICAL PROTOCOL (HRP-590)

PROTOCOL TITLE: Brivaracetam to Reduce Neuropathic Pain in Chronic SCI: A Pilot Clinical Trial  
VERSION DATE: 03/18/2024

steps will be performed in the Statminer software suite: quality control of biological replicates, filtering of miRNAs expression having Ct values below cycles and the detection of expression in all biological replicates of calibrator and target. Statistically significant miRNAs will be selected based on stringent parameters such as Benjamin-Hochberg false discovery rate (FDR) and data will be conservatively selected with adjusted p-values and p-value lower than 0.01 and 0.05, respectively. Functional pathway analysis of altered miRNAs and their association with proteins related to reduction in neuropathic pain will be performed using Ingenuity Pathway Analysis (IPA) program (Ingenuity Systems Inc., Redwood City, CA). This software compiles known interactions for relevant miRNAs potential/ targets from published literature. This does not involve detection of genotypes, mutations, or chromosomal changes. For clinical correlation analysis, data comparing changes in miRNA expression will be described as means with standard error of the mean. In order to analyze the differences between group means we will use analysis of variance (ANOVA) after the assessing for distribution and variance. Multiple comparisons will be performed using Games-Howell test.

### 15.2 Power Analysis:

Part of the goal of this pilot study is to obtain information that can be used for formal sample size estimation, including effect sizes and standard error estimates; therefore, analyses are included here that may not be included in a non-pilot follow-up (including the randomization analyses described below); further, some of the analyses here are exploratory to help in the design of a follow-up study. Also, (1) robust standard errors will be used in all cases to help guard against the effects of heteroskedasticity; (2) although there are a number of outcomes and, therefore, analyses, no adjustments for multiple comparisons will be made in this pilot study as the prime aim is not the level of statistical significance but rather the estimation of results needed for planning a follow-up. Of course, when disseminating our findings we will report the number of tests performed and the actual p-values so that readers can make their own adjustments if wanted.

### 15.3 Statistical Analysis:

All statistical analyses will be conducted with Stata v. 16 (Copyright 1985-2019 StataCorp LLC, College Station, TX) or SAS v.9.4 (Copyright (c) 2002-2012 by SAS Institute Inc., Cary, NC, USA) assuming a 5% level of significance unless otherwise stated. Participant characteristics will be

## MEDICAL PROTOCOL (HRP-590)

PROTOCOL TITLE: Brivaracetam to Reduce Neuropathic Pain in Chronic SCI: A Pilot Clinical Trial  
VERSION DATE: 03/18/2024

described using frequency counts and percentages (nominal variables) and means/standard deviations (SDs) or medians and interquartile ranges (IQRs) (continuous variables). Chi-square tests and t-tests or rank-sum tests will be used to compare the participant characteristics between the treatment arms.

### 15.4 Data Integrity:

Study staff will collect and store data. Data will be collected electronically or on paper forms. All electronic data will be stored on Box Secure Storage or REDCap. Paper forms will only be accessible by the study staff, trained study coordinator, and the principal investigator. All paper documents will be kept in locked file cabinets in locked offices at all times. Participant names, contact information, health history, and other information that can be traced back to the participant will be kept separately from data collected for the study. Personal information will be kept in a locked office and away from data or in a separate folder on Box Secure Storage. Collected data will have the participant's identification code and some computer software used to collect data will have the date and time marked on the file. Protocol sheets used during data collection will only have the participant's ID.

Imaging data (MRI scan results) will be identified by study ID without personal identifiers and stored on the system drive behind the institutional firewall or on Box Secure Storage. Some institutions consider MRI of the brain to contain identifiers due to the presence of facial features. We will not use software to mask facial features, therefore identifiable MRI data will be shared with [name] for analysis. All computers are password-protected and will only be used by trained study staff and for study purposes only.

All study records will be kept indefinitely after the study is closed. Research records will be stored in a manner to protect the confidentiality of participant information.

[name] will review data monthly. She will be responsible for monitoring the completeness of all data and source documents as well as monitoring the informed consent procedures. Checklists and note pages are used to note any deviations or omissions from the protocols. Any deviation to the protocol that may have an effect on the safety or rights of the volunteer or the integrity of the study will be promptly reported to the IRB.

MEDICAL PROTOCOL (HRP-590)

PROTOCOL TITLE: Brivaracetam to Reduce Neuropathic Pain in Chronic SCI: A Pilot Clinical Trial  
VERSION DATE: 03/18/2024

**16.0 Health Information and Privacy Compliance**

*16.1 Select which of the following is applicable to your research:*

- My research does not require access to individual health information.
- I am requesting that all research participants sign a HIPCO approved HIPAA Disclosure Authorization to participate in the research (either the standalone form or the combined consent and HIPAA Authorization).
- I am requesting the IRB to approve a Waiver or an alteration of research participant authorization to participate in the research.

Appropriate Use for Research:

*16.2 Identify the source of Private Health Information you will be using for your research (Check all that apply)*

- I will use the Informatics Consulting Services (ICS) available through CTSI (also referred to as the University's Information Exchange (IE) or data shelter) to pull records for me
- I will collect information directly from research participants.
- I will use University services to access and retrieve records from the Bone Marrow Transplant (BMPT) database, also known as the HSCT (Hematopoietic Stem Cell Transplant) database.
- I will pull records directly from EPIC.
- I will retrieve record directly from axiUm / MiPACS
- I will receive data from the Center for Medicare/Medicaid Services
- I will receive a limited data set from another institution
- Other. Describe:

A pre-screening phone survey will be completed and stored in paper format and REDCap to determine eligibility. After consent a health survey will be collected in paper format and stored in the participants study file.

*16.3 Explain how you will ensure that only records of patients who have agreed to have their information used for research will be reviewed.*

MEDICAL PROTOCOL (HRP-590)

PROTOCOL TITLE: Brivaracetam to Reduce Neuropathic Pain in Chronic SCI: A Pilot Clinical Trial  
VERSION DATE: 03/18/2024

The team will access PHI for screening purposes according to institutional policies. The team will access and record PHI for data collection only after receiving permission from each enrolled study participant.

16.4 Approximate number of records required for review: 25

16.5 Please describe how you will communicate with research participants during the course of this research. Check all applicable boxes

- This research involves record review only. There will be no communication with research participants.

I will use a desktop or laptop not previously listed

I will use an external hard drive or USB drive ("flash" or "thumb" drives) not previously listed

I will use a mobile device such as a tablet or smartphone not previously listed

## MEDICAL PROTOCOL (HRP-590)

PROTOCOL TITLE: Brivaracetam to Reduce Neuropathic Pain in Chronic SCI: A Pilot Clinical Trial  
VERSION DATE: 03/18/2024

### 16.8 Consultants. Vendors. Third Parties: -

#### *LC Sciences*

We will send blood serum samples to LC Sciences (Houston, TX) to perform microRNA analysis (non-genomic analysis). LC Sciences will have access to de-identified data only.

#### *REDCap eConsent*

The informed consent form and HIPAA form will be signed with an eSignature using REDCap. The REDCap eConsent process is a 21 CFR Part 11 compliant method for electronic signature capture. For more information on REDCap compliance, please visit:

[https://redcap.ahc.umn.edu/surveys/?s=3PT9FY73NC&topics\\_\\_\\_ec=1#ec](https://redcap.ahc.umn.edu/surveys/?s=3PT9FY73NC&topics___ec=1#ec)

### 16.9 Links to identifiable data:

The research data will be collected on RedCap and on the MRI. Those data will not contain personal identifiable information. Only the PI/Co-PI will have a document that links the name with the code, which will be kept secure on the University Box secure storage.

### 16.10 Sharing of Data with Research Team Members:

Only deidentified data will be shared with team members. The PI and clinical trial coordinator will have access to identifiable information for contact purposes.

### 16.11 Storage and Disposal of Paper Documents:

Documents will be stored in a secure closet behind secure doors in the PI and Co-PI's offices and labs. Documents that need to be disposed will be disposed of in secure bins and then shredded.

## 17.0 Confidentiality

### 17.1 Data Security:

Clinical data will be stored on Research Electronic Data Capture (REDCap) and on HIPAA protected encrypted servers. Participant confidentiality will be safeguarded by password protected databases and locked file cabinets. Research records will be stripped of identifying information, with keys identifying participants available only to the PI or selected study-related personnel who have met the necessary Responsible Conduct of Research, HIPAA, human participants, data security and study specific training requirements. Brain imaging will be acquired via standardized protocols. MRI data acquisition will not contain personal health information. The MRI

MEDICAL PROTOCOL (HRP-590)

PROTOCOL TITLE: Brivaracetam to Reduce Neuropathic Pain in Chronic SCI: A Pilot Clinical Trial  
VERSION DATE: 03/18/2024

data be stored in digital form behind institutional firewalls or on Box Secure Storage.

Information about study participants will be kept confidential and managed according to the requirements of the Health Insurance Portability and Accountability Act of 1996 (HIPAA). Those regulations require a signed participant authorization informing the participant of the following:

- What protected health information (PHI) will be collected from participants in this study
- Who will have access to that information and why
- Who will use or disclose that information
- The rights of a research participant to revoke their authorization for use of their PHI.

In the event that a participant revokes authorization to collect or use PHI, the investigator, by regulation, retains the ability to use all information collected prior to the revocation of participant authorization. For participants that have revoked authorization to collect or use PHI, attempts should be made to obtain permission to collect at least vital status (i.e. that the participant is alive) at the end of their scheduled study period.

Procedures are in place for maintaining the full confidentiality of all information collected. Participant confidentiality will be protected by securing all hard copy study files in locked filing cabinets. Electronic files containing personal identifiers will be stored on Box Secure Storage or REDCap. All study staff receive training on privacy standards for maintaining participant confidentiality. All published reports will be of summary nature and no individual participants will be identified beyond the investigative staff involved in the project.

REDCap includes a complete suite of features to support HIPAA compliance, including a full audit trail, user-based privileges, and integration with the institutional LDAP server. The MySQL database and the web server will both be housed on secure servers operated by the UMN Academic Health Center's Information Systems group (AHC-IS). The servers are in a physically secure location on campus and are backed up nightly, with the backups stored in accordance with the AHC-IS retention schedule of daily, weekly, and monthly tapes retained for 1 month, 3 months, and 6 months, respectively. Weekly backup tapes are stored offsite. The AHC-IS servers provide a stable, secure, well-maintained, and high-capacity data storage environment, and both REDCap and MySQL are widely-used,

## MEDICAL PROTOCOL (HRP-590)

PROTOCOL TITLE: Brivaracetam to Reduce Neuropathic Pain in Chronic SCI: A Pilot Clinical Trial  
VERSION DATE: 03/18/2024

powerful, reliable, well-supported systems. Access to the study's data in REDCap will be restricted to the members of the study team by username and password.

The informed consent form and HIPAA form will be signed with an eSignature using REDCap. The REDCap eConsent process is a 21 CFR Part 11 compliant method for electronic signature capture. For more information on REDCap compliance, please visit:

[https://redcap.ahc.umn.edu/surveys/?s=3PT9FY73NC&topics\\_\\_\\_ec=1#ec](https://redcap.ahc.umn.edu/surveys/?s=3PT9FY73NC&topics___ec=1#ec)

Data files will be stored locally at the UMN Department of Rehabilitation Medicine. All data are stored on a secure HIPAA protected PC, and on secure HIPAA protected servers (Box Secure Storage). Raw and processed brain imaging data are also stored by the biostatistician/brain imaging analysis specialists responsible for brain analysis and are backed up weekly.

Training: All study staff will be appropriately trained in data security.

Authorization of access: Only designated IRB-approved staff will have access to the data.

Password protection/encryption/physical controls: All data will be stored in REDCap/Box.

Separation of Identifiers: Study staff will keep the mapping of identification code to the identity of the participant in a database protected by two-levels of password protection stored separately from the data on Box

## **18.0 Provisions to Monitor the Data to Ensure the Safety of Participants**

### *18.1 Data Integrity Monitoring.*

This trial will be conducted in compliance with this protocol, good clinical practice, and the applicable regulatory requirements. Further monitoring will be completed by a CTSI monitor that will be assigned to the study.

Study Oversight. Continuous study oversight will be provided by the study PIs, [name], Swedish Medical Center/Craig Hospital site PI, and Drs. [name] and [name], UMN site PI and Co-I, Department of Rehabilitation Medicine, University of Minnesota.

Plan for Data Management. Data will be collected electronically (imaging files) or on paper forms. All electronic data will be stored on Box Secure Storage or REDCap. Paper forms will only be accessible by the study staff,

## MEDICAL PROTOCOL (HRP-590)

PROTOCOL TITLE: Brivaracetam to Reduce Neuropathic Pain in Chronic SCI: A Pilot Clinical Trial  
VERSION DATE: 03/18/2024

trained study coordinator, and the principal investigator. All of these documents will be kept in locked file cabinets in locked offices at all times. Participant names, contact information, health history, and other information that can be traced back to the participant will be kept separately from data collected for the study. Personal information will be kept in a locked office and away from data. Collected data will have the participant's identification code and some computer software used to collect data will have the date and time marked on the file. Protocol sheets used during data collection will only have the participant's ID.

MRI imaging data will be identified by study ID without personal identifiers and stored on the system drive behind the institutional firewall. All computers are password-protected and will only be used by trained study staff and for study purposes only.

All study records will be kept indefinitely after the study is closed. Research records will be stored in a manner to protect the confidentiality of participant information.

### 18.2 Data Safety Monitoring

Plan for Monitoring Safety. The safety environment of UMN participants will be overseen and monitored by [name]. We will monitor to assure that participants meet eligibility criteria; that the informed consent process is conducted appropriately, that the data will be collected and analyzed as specified in the protocol, that adverse events (defined below) are reviewed promptly and reported as required (detailed below), that dropouts are documented, and that primary and secondary endpoints are evaluated. According to the data safety-monitoring plan, study participation will be terminated immediately in the event of injury or increased morbidity (drug intolerance). Data and all procedures will be monitored at each measurement time point and monthly throughout the duration of the study to ensure the safety of participants.

Unblinded Study Physician/Medical Monitor. Our safety monitoring plan also includes an independent medical monitor: [name] (Thomas Jefferson University). [name] will review all reported adverse events on a monthly basis and as needed with the PI, [name], who will inform [name] immediately of all study-related unanticipated problems involving risk to volunteers or others, serious adverse events, and all volunteer deaths associated with the protocol, and provide an unbiased written report of the event to the IRB and FDA. The medical monitor will comment on the outcomes of the event or problem, and in the case of a serious adverse event or death, comment on the relationship to

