### **3.0 Study Endpoints/Events/Outcomes**

#### **3.1 Primary Endpoint/Event/Outcome:**

Our primary endpoints will be 1) safety as determined by number of drug related adverse events and assessed through weekly adverse event screening by phone, and 2) efficacy as determined by reduction in pain intensity assessed by the Brief Pain Inventory. We will use the clinically meaningful reduction in Brief Pain Inventory score of 1 point or more as the definition of “drug response” in this study.

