## 5.0 Procedures Involved

### 5.1 Study Design:

This is a multi-center randomized, double-blinded placebo-controlled pilot clinical trial. Each site (Swedish Medical Center/Craig Hospital, UMN) will enroll and study 20 adults, 18 years of age and older with SCI. [name] will serve as PI, and [name] will serve as Co-I at UMN (local site). MRI data analysis will be conducted by [name] (Harvard University). [name] will receive a deidentified dataset and will have no human subject interactions. Research activities at the Swedish Medical Center/Craig Hospital will be conducted under a separate IRB protocol at Craig Hospital.

Participants who meet the eligibility criteria will be randomly assigned to active drug (escalating brivaracetam dose to 100 mg twice daily for 3 months) or placebo based on a randomization schedule developed by our biostatistician. This is a simple computer generated 1:1 scheme that randomly assigns participants to arm A or arm B. Study participants, research coordinators, and study personnel involved in outcomes assessments and analyses will all be blinded. The drug will be provided by RxArtisans pharmacy in Wayzata, MN. The active and placebo capsules will have identical appearance and consistency. Treatment assignment will be known only to the investigational drug pharmacies (RxArtisans). We have registered this pilot study with National Institutes of Health (NIH) clinical trials registry, [www.clinicaltrials.gov](http://www.clinicaltrials.gov) (NCT04379011). The pilot data generated by this effort will be used to power a subsequent multi-center clinical trial.

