CDE-recommended questionnaires relating to pain, mood, active suicidality, satisfaction with life, kinesiophobia, sleep quality, and community integration will be administered. Participants will then begin 3 months of active treatment (100 mg BID) or placebo. All participants will receive a medication diary to track study drug compliance and to record medication use. Blinded data collectors will perform weekly check-in calls to assess for medication-related adverse events including the PHQ-9 for changes in mood and suicidality. Reported AEs identified in these calls will be documented and immediately shared with the PI for review.

End of study assessments will be repeated 3 months after baseline testing and again 1 month after cessation of study medication (active/placebo).

Lab work will be repeated to confirm normal renal function, absence of liver cirrhosis, and absence of pregnancy in individuals of childbearing potential at the end of the study. Specimen collection and analysis will either occur at the Fairview Clinical Research Unit or with the participant's

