## MEDICAL PROTOCOL (HRP-590)

PROTOCOL TITLE: Brivaracetam to Reduce Neuropathic Pain in Chronic SCI: A Pilot Clinical Trial  
VERSION DATE: 03/18/2024

participation in the study. The medical monitor will also indicate whether he concurs with the details of the report provided by the study investigator. Reports for events determined by either the investigator or medical monitor to be possibly or definitely related to participation, and reports of events resulting in death will be promptly forwarded to the IRB and FDA.

Reporting Adverse Events. Anticipated adverse events (detailed above in 13.0, Risks to Participants) will be identified while interviewing participants, during physical exams, and while reviewing laboratory results. Participants also will be directed to call study staff to report adverse events that may occur between these visits. All adverse events will be noted on the Adverse Events log form that will be kept in the participant's file. Unanticipated adverse events and unanticipated serious adverse events (as defined in CFR Title 21), also will be identified during testing time points and through participant self-reporting between these visits. They will be noted on the Adverse Events Log and promptly brought to the attention of the study PI.

Unanticipated serious adverse events will be reported within 5 working days to the UMN IRB as required.

Follow-up of Adverse Events. In the unlikely event that a participant is injured as a result of this research study, medical care, including emergency treatment will be provided.

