Assessment of Risk. This is a moderate risk pilot clinical study. As such, our safety monitoring plan will include a medical monitor: [name]. [name] will review all reported adverse events on a monthly basis with [name], the medical monitor. Additionally, [name] will inform [name] immediately of all study-related unanticipated problems involving risk to volunteers or others, serious adverse events, and all volunteer deaths associated with the protocol, and provide an unbiased written report of the event to the IRB. The medical monitor will comment on the outcomes of the event or problem, and in the case of a serious adverse event or death, comment on the relationship to participation in the study. The medical monitor will also indicate whether he concurs with the details of the report provided by the study investigator. Reports for events determined by either the investigator or medical monitor to be possibly or definitely related to participation, and reports of events resulting in death will be promptly forwarded to the IRB.

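### Sections 5.1 and 18.2 disagree on who knows treatment assignment, and nothing reserves the causality call behind the primary safety endpoint for a blinded assessor

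*Combined protocol and SAP*

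**What the plan says.** On who holds the assignments, Section 5.1 (Study Design) is categorical: "Treatment assignment will be known only to the investigational drug pharmacies (RxArtisans"). It adds that "Study participants, research coordinators, and study personnel involved in outcomes assessments and analyses will all be blinded". The PI, the study physician and the medical monitor are not named in that list.

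Section 18.2 (Data Safety Monitoring) has a paragraph headed "Unblinded Study Physician/Medical Monitor". The person described there, called independent, "will review all reported adverse events on a monthly basis and as needed with the PI". The monitor is also to state agreement or disagreement with the investigator's report and, "in the case of a serious adverse event or death, comment on the relationship to participation in the study". The same section provides that "Reports for events determined by either the investigator or medical monitor to be possibly or definitely related to participation" are sent on promptly to the regulatory bodies.

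Section 3.1 defines the first primary endpoint as "safety as determined by number of drug related adverse events and assessed through weekly adverse event screening by phone", and Section 5.2 repeats it in short form. Section 5.2 also says that "Blinded data collectors will perform weekly check-in calls to assess for medication-related adverse events" and that what they find goes at once to the PI.

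**The concern.** The safety endpoint is a count of events attributed to the drug, not of all events. Attribution is a judgement, and it is open to influence from knowledge of the arm. A physician who knows that a participant is taking active drug may more readily attribute sleepiness or irritability to it than one who knows that the participant is on placebo. The same events could then give different counts in the two arms with no true difference between them.

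The protocol contains one role labelled as unblinded, and that role takes part in the only relatedness process it describes. The reviews are held with the PI, who receives every event from the weekly calls and, under the study drop criteria in Section 5.2, supervises dose reduction for intolerance. If assignments passed to the PI in those reviews, the blind would be weakened at the centre of the trial. The pilot is meant to inform a larger trial, so a distorted safety comparison would carry forward into its design.

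**Working it through.** No arithmetic applies: the plan gives no figure on this point, and no event count or attribution rate from which to derive one. The check sets the statements side by side.

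1. **Access to assignments.** Section 5.1 limits knowledge to the pharmacy, without exception. Section 18.2 names an unblinded physician/monitor. There are two ways to read this.
   - The word in the heading is a leftover. Section 5.1 then stands and the contradiction disappears once the word is deleted.
   - The word is intended. Section 5.1 is then wrong as written, and the plan needs to say how and when the monitor is unblinded and who else may learn the assignment. It says neither.

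2. **The path of one adverse event.**
   - Collection: a blinded data collector, by weekly call (Section 5.2). This step is protected.
   - First review: the PI (Section 5.2). The PI's blinding is not stated.
   - Joint review: the PI with the monitor (Section 18.2). No rule says whether the listings show arm, or whether the monitor may disclose it.
   - Relatedness for reporting: either the investigator or the monitor may determine it (Section 18.2).
   - Relatedness for the endpoint count: no one is named. Sections 3.1 and 5.2 define the endpoint without naming an assessor, and Section 15 does not say how events are classified for the count.

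3. **Reach of the monitor's role.** The express duty to comment on relationship covers serious events and deaths only. The relationship is to study participation, which is not the same as relationship to the drug. The clause that lets either party determine relatedness is not confined to serious events, but its stated consequence is forwarding a report. No sentence links it to the endpoint.

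4. **Reach of the blinding rule.** The Section 5.1 sentence on personnel involved in outcome assessment could be read to cover whoever attributes events, since drug-related events are a primary outcome. It does not mention causality. The only relatedness process in the protocol is the one in Section 18.2, which includes the role labelled as unblinded.

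The result is one direct contradiction (step 1) and one unassigned judgement (the last stage of step 2). Steps 3 and 4 show that the text neither gives that judgement to the unblinded monitor nor clearly keeps it from that role.

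**The case against.** The strongest reply is that the protocol's general rule is blinded assessment. Section 5.1 calls the trial double-blinded and blinds those who assess outcomes, and Section 5.2 blinds those who collect adverse events. An independent safety monitor with access to assignments is acceptable practice and not a flaw in itself. The word at issue appears once, in a paragraph heading. The text below that heading, the later paragraph on assessment of risk and Section 24.3 all describe the monitor without it. All of this stands, and it limits the point.

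Three stronger readings are tempting, and the documents do not support them.

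- *A reader might infer that the unblinded monitor decides the primary safety endpoint.* The monitor's stated roles are to comment on serious events and deaths and to share in a determination that triggers reporting. Neither is tied to the count.
- *A reader might infer that the PI is unblinded through the reviews.* Discussing events with someone who knows the assignments does not in itself reveal them. No sentence says that listings carry the arm or that the monitor shares it. A further effect on pain scores is more remote, since pain is self-reported by participants who are blinded.
- *A reader might infer that an unblinded person treats participants*, because the heading joins study physician to medical monitor and Section 12.2 has a study physician help with tapering at withdrawal. Sections 18.2 and 24.3 call the monitor independent and external, and the text does not settle whether the roles coincide.

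What the reply does not answer is that blinded collection protects the recording of events, not their attribution. Whichever way the heading was meant, the text has to change.

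**Conclusion.** The point holds in a limited form. Sections 5.1 and 18.2 make statements about access to assignments that cannot both be true. In addition, the protocol does not say who makes the drug-relatedness call for a primary endpoint, whether the PI is blinded, or that the monitor must not disclose assignment. Together these leave open a route by which knowledge of arm could enter the primary safety comparison.

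The size of any bias cannot be estimated. The documents give no expected number of events, no attribution rate and no account of how often the monitor would see an assignment, so any figure would be invented. The conclusion rests on the text alone and assumes only that causality attribution can be influenced by knowledge of arm. It does not assume that such influence occurred. The change is worth making because it resolves a plain contradiction and protects a primary endpoint at very little cost. It is not a reason to remove the monitor or to restrict the monitor's access to assignments.

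**What to change.** Reconcile Sections 5.1 and 18.2, and add a sentence on the endpoint to Section 3.1:

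- In Section 5.1, list every person or role with access to assignments. If the word in the Section 18.2 heading is a leftover, delete it there instead.
- State that the PI, site investigators and outcome assessors are blinded.
- State that the primary safety endpoint uses only the drug-relatedness recorded by a blinded investigator before any unblinded review, and that the monitor's determination serves safety reporting only.
- State that reviews with the PI use listings without arm, and that the monitor does not disclose assignment to the PI or site staff.

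The Revision History entry for version 8.0 notes that enrolment is complete, so part of this must be done in retrospect. Document who had access to assignments during the trial. Where causality was not recorded blind, have a blinded investigator assign it from arm-masked records before analysis.

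The cost is a few sentences and one arm-masked listing, with no extra staff. The retrospective step adds a single pass through the adverse event records, and only where blinded causality is missing.
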